5.5 Subject Withdrawal from the Clinical Study

A subject may withdraw from the clinical study at any time and for any reason, and should notify the Investigator in this event. Subjects are not obligated to reveal their reasons for withdrawal. The subject will be withdrawn if he/she relocates to another geographic area that requires a change of physician and such suitable physician cannot be identified.

The Investigator may withdraw the subject from the clinical study at any time based on his/her medical judgment. It is important that the Investigator encourage subjects to return for all required follow-up visits within the designated window. The clinical study objectives may not be realized if a significant number of subjects are lost to follow-up. A subject may withdraw, or be withdrawn by the Investigator, if he or she is unable to continue participation in the study due to any condition unrelated to the study.

The Investigator or designee must complete the appropriate CRF (Study Completion/Discontinuation Form) documenting the subject's withdrawal or discontinuation from the clinical study. The subject will be considered withdrawn once the Sponsor receives the respective CRF.

At any time other than the immediate index procedure during the study where complications prevent retention of the GORE® Septal Occluder (i.e., embolization or other event requiring device removal), the subject will be discontinued from further study follow-up. All adverse events will be collected and reported in compliance with this protocol through the point of device removal. The Investigator or designee will complete the Study Completion/Discontinuation Form documenting the subject's discontinuation from the clinical study.

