5.6 Subject Lost to Follow-Up

A subject will be considered lost to follow-up and terminated from the study once they have missed at least one follow-up visit or at the discretion of the Investigator or Sponsor, and three documented attempts have been made by the Investigator or designee to contact the subject or legally authorized representative. One of the three documented attempts must include a certified letter.

CONFIDENTIAL INFORMATION

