10.6.2 Analysis Populations

The analysis populations for the study are:

- Per-Protocol (primary analysis population) – this population will include enrolled subjects who had no inclusion/exclusion

CONFIDENTIAL INFORMATION

violations and who complete evaluation through the 6-month follow-up.

- Intent-to-treat – this population will include all enrolled subjects.

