10.6.3 Statistical Analysis of Primary Endpoint

The primary endpoint analysis will be a comparison of the proportion of subjects who meet the composite Clinical Success requirements through the 6-month follow-up between the study population and the historical control population of GORE® HELEX Septal Occluder studies. The primary analysis population will be the per-protocol population. The primary endpoint will be compared using a two-sample binomial proportions test with a non-inferiority margin of 10%. In statistical terms:

$$z = \frac{p_C - p_T - \Delta}{\sqrt{\frac{p_C(1-p_C)}{n_C} + \frac{p_T(1-p_T)}{n_T}}}$$

where:

p_C = observed Clinical Success proportion at 6 months in control group

n_C = number of subjects with primary endpoint evaluation in control group

p_T = observed Clinical Success proportion at 6 months in test group

n_T = number of subjects with primary endpoint evaluation in test group

The test statistic z is assumed to have a standard Normal distribution. Based on the alpha ≤ 0.05 criterion, a result of $z < -1.64$ will result in rejection of the null hypothesis in favor of the alternative hypothesis and a conclusion that the GORE® Septal Occluder is not inferior to the current GORE® HELEX Septal Occluder.

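### A subject whose follow-up ends before the 6-month evaluation leaves the primary test, even if already a failure, so outcome-linked withdrawal could bias the result toward non-inferiority

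*Combined protocol and SAP*

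**What the plan says.** **Ending follow-up.** Section 5.5: "The Investigator may withdraw the subject from the clinical study at any time based on his/her medical judgment". A discontinuation form must be completed; no list of criteria or second review is attached. Under 5.6 a subject is lost after missing at least one visit, or "at the discretion of the Investigator or Sponsor, and three documented attempts have been made by the Investigator or designee". It adds: "One of the three documented attempts must include a certified letter". Section 5.5 also requires that a subject whose occluder is lost or removed after the index procedure be discontinued from further follow-up.

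**Who is analysed.** Section 10.6.3: "The primary analysis population will be the per-protocol population". By 10.6.2 that set is enrolled subjects with no inclusion/exclusion "violations and who complete evaluation through the 6-month follow-up". The denominator n_T is the "number of subjects with primary endpoint evaluation in test group". For intent-to-treat, 10.6.2 says "this population will include all enrolled subjects", but no analysis of the primary endpoint, missing-data rule or sensitivity analysis is assigned to that population.

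**What counts as failure.** Under 3.2.1 a subject can fail well before 6 months: no device retained at the end of the procedure, an SAE through day 30, or a device event. Only the residual-shunt component needs the 6-month echo, which the Echo Core Lab reads.

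**The concern.** Completion of the 6-month evaluation is a condition for entering the primary test, and staff who know how the subject is doing can affect whether it is met. The study is single-arm, so the investigator knows the device. Echo is scheduled at pre-discharge and at 30 days (5.2), and the investigator judges whether each adverse event is serious (9.4). The control data come from studies already done, so selective removal can act only on the test group.

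The stated error rate in 10.6.3 holds if removal is unrelated to outcome. If subjects who have failed, or look likely to fail, are withdrawn more often, p_T rises and the z statistic moves toward rejection with no change in device performance. The literal completer rule makes this worse, because it also excludes subjects whose failure is already on record. Those whose occluder is removed between the procedure and 6 months are an example: 3.2.1 makes them failures, 5.5 discontinues them, and 10.6.2 then leaves them out.

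**Working it through.** **1. The plan's own figure.** Inputs from 10.4: n_C = 253, both rates 86.6%, margin 10%, alpha 0.05 (used one-sided, z < -1.64).

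SE = sqrt(0.866 × 0.134 × (1/253 + 1/135)) = 0.0363. Power = Φ(0.10/0.0363 − 1.645) = Φ(1.109) = 0.866, matching the stated ≥0.86 at 135 evaluable. Then 135/0.90 = 150 enrolled. The design reproduces.

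**2. The control count.** Table 10.2.1 is redacted, so the count is inferred: 0.866 × 253 = 219.1, taken as 219. Checks: 219/253 = 86.6%; lower 95% bound 0.8656 − 1.96 × sqrt(0.8656 × 0.1344/253) = 82.4% (10.3 states 82%); adding the 18 missing echoes as failures, 219/271 = 80.8% (10.3 states 81%). So 86.6% appears to be a complete-case rate.

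**3. How few removals change the result.** From 10.6.3, z = (p_C − p_T − 0.10)/sqrt(p_C(1−p_C)/253 + p_T(1−p_T)/n_T), with p_C = 219/253. At n_T = 135 the pass mark is 112 successes (z = −1.649; 111 gives −1.441).

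| Observed | z | After removing failures | z |
|---|---|---|---|
| 111/135 (82.2%) | −1.44, fails | 2 removed: 111/133 | −1.78, passes |
| 110/135 (81.5%) | −1.24, fails | 3 removed: 110/132 | −1.74, passes |
| 108/135 (80.0%) | −0.85, fails | 5 removed: 108/130 | −1.66, passes |
| 115/150 (76.7%) | −0.03, fails | 12 removed: 115/138 | −1.77, passes |

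The last row starts at about the margin. Its 12 removals are 8% of 150, inside the 10% loss the plan allows for.

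**4. False non-inferiority rate.** The true test rate is set at the margin, 86.6% − 10% = 76.6%, with 135 subjects. Each failure is removed independently with probability f, then z < −1.64 is applied. About 135 × 0.234 = 31.6 failures are expected, so f = 10% is about 3 subjects.

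| f (assumed) | Control drawn from Binomial(253, 0.866) | Control held at 219/253 |
|---|---|---|
| 0 | 5.8% | 4.6% |
| 5% | 8.7% | about 6% |
| 10% | 12.8% | about 10% |
| 20% | 25% | about 23% |

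The first column is the unconditional error rate; the second is conditional on the control result already observed.

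**5. Contrast with unrelated loss.** Random loss of 10% of 150 subjects, control redrawn, leaves the rate at 5.8%. The inflation comes from the link to outcome, not from loss as such.

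**The case against.** - **The protocol works against loss.** Sections 5.4.8 and 5.5 ask investigators to encourage return visits, 5.4.9 keeps a subject with a reintervention and a retained occluder in follow-up, a discontinuation form is required, and sites are monitored. This makes casual removal less likely. It does not change how a withdrawn subject is analysed.
- **The investigator does not decide the shunt endpoint.** The Echo Core Lab does, at 6 months, so a 30-day echo is only a predictor. That stands for the shunt component. SAE status by day 30 is known to the investigator, and the Core Lab cannot read an echo that was never obtained.
- **The simulation removes from all failures.** These include unsuccessful implants, which 5.4.6 treats as enrolled technical failures. The share of failures open to removal is unknown, so the table shows sensitivity and is not a forecast.
- **Known failures may be meant to stay in.** Section 5.4.6 suggests so for unsuccessful implants. But 10.6.2 has no such exception, and these subjects are discontinued after a 30-day call.
- **Medical-judgement withdrawal has a proper use.** It can spare a subject study procedures such as the fluoroscopy required in the first 150 subjects. This stands, and it is why the clause itself should not be the target.

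A reader might also infer that the sponsor can drop a subject simply by choosing to. The words "at the discretion of the Investigator or Sponsor" do appear in 5.6, but they are joined to three documented attempts, one including a certified letter. Nor does every withdrawal matter here: one after the 6-month evaluation leaves the primary test unchanged.

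**Conclusion.** The concern holds, and its statistical cause is the completer rule in 10.6.2 and 10.6.3. The withdrawal clauses only supply the route. Near the pass mark, two to five outcome-linked removals out of 135 would reverse the primary conclusion. At the margin, removing 10% of failures roughly doubles the false non-inferiority rate (5.8% to 12.8% with the control redrawn; 4.6% to about 10% with it fixed).

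This rests on the inferred control count of 219/253, on independent removal of failures, and on assumed removal fractions that no figure in the documents supports. It also rests on reading 10.6.2 literally. The documents do not show that selective removal is intended or likely; the figures show what the plan leaves open. The change is worth making because no all-enrolled analysis of the primary endpoint is specified that would expose the effect.

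**What to change.** Leave the withdrawal clauses in 5.5 and 5.6 as they are. In 10.6.2 and 10.6.3:

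(a) Keep in n_T, as a failure, any enrolled subject who met a failure criterion of 3.2.1 before follow-up ended, whatever the completion status.

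(b) Count as a failure any subject with a retained occluder whose follow-up was ended by the investigator or sponsor before the 6-month evaluation.

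(c) Report an all-enrolled analysis with missing counted as failure in both groups (HELEX 81%, from 10.3), or a tipping-point analysis, and list the reason and timing of each withdrawal.

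**Cost.** A wording amendment and one further analysis; consent rights and clinical care are untouched. A few true successes may be scored as failures under (b), and (b) is conservative against a control rate that appears to be complete-case, so that asymmetry should be stated.

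The two-group version of (c) is not automatically stricter. With the control at 219/271, z at 117/150 is (0.8081 − 0.7800 − 0.10)/sqrt(0.8081 × 0.1919/271 + 0.78 × 0.22/150) = −1.74, a pass, whereas 125/150 is needed against 219/253. It should therefore be read beside the primary result, and a tipping-point analysis may be more informative.

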5.6 Subject Lost to Follow-Up

A subject will be considered lost to follow-up and terminated from the study once they have missed at least one follow-up visit or at the discretion of the Investigator or Sponsor, and three documented attempts have been made by the Investigator or designee to contact the subject or legally authorized representative. One of the three documented attempts must include a certified letter.

CONFIDENTIAL INFORMATION

5.7 Subject Study Completion

A subject has completed the study when the 36 month follow-up visit has been completed. Any subject who does not complete the 36 month follow-up visit due to voluntary withdrawal, physician withdrawal, death or any other reason will be considered a withdrawal. Subjects will not be provided with any medical care by the Sponsor after study completion or withdrawal.

5.8 Explant Procedures

The GORE® Septal Occluder may be explanted during a surgical procedure or as part of an autopsy. Investigative Centers are requested to return explanted device to W. L. Gore & Associates, Inc. for gross and histological evaluation. Prior to planned or potential device retrieval, contact the GORE® Septal Occluder Study Manager to communicate that a specimen is being retrieved from a study subject. A specimen shipping kit will be sent immediately to the Investigative Center. The specimen kit provides specific packaging and handling instructions for the specimen and contains a shipping container.

6.0 Clinical Study Administration

6.1 Training

Participating Investigators are required to complete device didactic and protocol training prior to first implant. The first study implant is observed by a Gore representative and is considered a clinical training case.

6.2 Device Accountability and Storage

The GORE® Septal Occluder may be used only under the supervision of the Investigator and in strict accordance with this protocol and applicable laws and regulations. The occluder may be implanted only in subjects who meet the inclusion/exclusion criteria set forth in this protocol. The Investigator will maintain accurate, detailed records of all devices received from Sponsor. The Investigator will record and maintain records of each device used on the corresponding CRF, and will notify Sponsor immediately if any devices are damaged or unaccounted for. The devices must be accessible only to the personnel involved in the study and stored in a secure facility.

Upon completion or termination of the clinical study or the Investigator's participation in the clinical study, or at the Sponsor's request, the Investigator will return any remaining supply of the device or dispose of the devices as directed by the Sponsor.

CONFIDENTIAL INFORMATION

6.3 Core Laboratory

All protocol prescribed imaging (screening/pre-procedure, procedure, pre-discharge, 30 days, and 6, 12 and 36 months) must be recorded in DICOM format, subject information de-identified by turning off the system overlay feature and replaced with study ID, and images uploaded to BioClinica WebSend secure web portal. The Core Laboratory will access images through the BioClinica web portal and evaluate prescribed intervals. Results of core lab evaluations will be available on the subject EDC records.

6.4 Study Monitoring

Clinical Investigative Site monitoring for this study will be provided by Theorem Clinical Research. Monitoring oversight will be provided by the Sponsor.

The Investigative Site monitors are qualified by training and experience to oversee the progress of the study at the site and will ensure that the Investigators and their staff understand and adhere to both the applicable regulatory requirements and the study protocol. In addition, they may assist in resolution of any problems that may arise during the study.

6.4.1 Monitoring Procedures

6.4.1.1 *Clinical Investigative Site Initiation Visit*

Site initiation will be performed to assure that each Investigator and his/her staff understands the protocol, applicable regulations, human subject protection requirements, and the Investigator's obligations. This visit will ensure that required documentation with the appropriate approval is in place prior to subject enrollment.

6.4.1.2 *Periodic Clinical Investigative Site Visits*

Periodic site visits will occur as necessary to ensure continuing adequacy of facilities and adherence to the clinical study protocol, the GCPs, and applicable regulations and laws that pertain to the conduct of the clinical study. During these visits, the monitor will also review the CRFs and source documentation, the timely submission of accurate records to the Sponsor, and the maintenance of proper records. A report will be written following each investigative site visit and a follow up letter will be provided to the site with a summary of findings.

6.4.1.3 *Clinical Monitor Reports*

The Sponsor's Clinical Monitor(s) will prepare a written report for the Sponsor following each investigative site visit. Reports will include

CONFIDENTIAL INFORMATION

specific information regarding observations made at the site visit, including staff members consulted, records reviewed, subject enrollment and general progress of the study, status of any problems identified, any correctional action recommended, and any other information deemed pertinent by the Sponsor's Clinical Monitor.

6.5 Protocol Deviations

A protocol deviation is defined as any change, divergence, or departure from the study design or procedures of a research protocol that is under the Investigator's control and that has not been approved by the IRB. The Investigator is responsible for reporting protocol deviations to their IRB per IRB policy and the Sponsor promptly. The Sponsor will determine the effect of the protocol deviation on the scientific soundness of the clinical study and subject safety and determine if additional reports or actions are required. Additional action may include site retraining, removal of devices from the site, and/or site termination.

The Investigator will not implement any changes to the protocol without first obtaining written agreement from the Sponsor and documented approval from the IRB, except in the event of an immediate hazard(s) to a subject.

6.6 Protocol Amendments

The Investigator will maintain a copy of the original protocol and all amendments. The Investigator will obtain IRB approval on all amendments in a timely manner. The sponsor will ensure proper training of Investigator and site staff on all protocol amendments as necessary.

6.7 Sponsor Representatives

Sponsor representatives may be present during study procedures to support the Investigator. The representatives may provide guidance for use of the device.

6.8 Source Documents and Access to Source Data

The Investigator will keep all study records, source data and investigational devices available for inspection by the Sponsor, Sponsor's monitors, and regulatory authorities.

Source data is defined as all information in original records, certified copies of original records of clinical findings, observations, or other activities in a clinical investigation necessary for the reconstruction and evaluation of the clinical investigation.

CONFIDENTIAL INFORMATION

6.9 Study Records Retention

The Investigator will maintain complete, accurate and current study records as required by applicable regulatory requirements. Records will be maintained during the clinical study and for a minimum of two years after the latter of the date on which the study is terminated or completed, or the date the records are no longer required to support regulatory approval of the device. In any event, clinical study records will not be disposed of, nor custody of the records transferred, without prior written Sponsor approval.

Investigator records will include, but are not limited to:

- All study-related correspondence with another Investigator, the IRB, the Sponsor, a Monitor, regulatory authority, or a study subject.
- Accountability records of receipt, use and disposition of all investigational devices including the type and quantity of the devices, the dates of their receipt, and the lot numbers. In addition, the names of all persons who received, used or disposed of each device.
- Subject records that include the subject's case history (e.g., medical records, reports of procedures, diagnostic tests and laboratory reports), the signed informed consent and process, and exposure to the device. In addition, all relevant observations, including records concerning adverse device effects, information and data on the condition of each subject upon entering and during the course of the investigation, and previous medical history should be retained. Pertinent information will be documented on standardized CRFs provided by the Sponsor.
- A copy of the study protocol and all amendments. Any deviations from the protocol will be documented.
- Reports and information pertaining to Unanticipated Adverse Device Effects (UADEs).
- All information pertaining to IRB review and approval of the clinical study. This includes a copy of the IRB approval or any subsequent renewal, the IRB-approved Informed Consent Form(s), and a certification stating that the IRB is in compliance with Food and Drug Administration (FDA) regulations.
- An original signed Investigator Agreement or equivalent.

The Investigator will prepare and submit the following reports:

CONFIDENTIAL INFORMATION

- IRB approval withdrawal: information pertaining to withdrawal of IRB approval will be provided to the Sponsor within five working days after the Investigator has been notified of the withdrawal.

Progress reports:

- Progress reports documenting the procedure, AEs and follow-up data concerning individual subjects will be submitted to the Sponsor on standardized CRFs. The Investigator may also be required to submit progress reports to the institutional IRB and to the Sponsor summarizing the Investigator's experience during the study.

Other:

- Any other reports as reasonably requested by the Sponsor or required by FDA.

6.10 Publication Plan

The International Committee of Medical Journal Editors (ICMJE) member journals have adopted a trials-registration policy as a condition for publication. This policy requires that all clinical trials be registered in a public trials registry. The Sponsor will register the study and post results as required by this policy and applicable U.S. laws and regulations.

It is the intent of the Sponsor that the multicenter results of this study will be submitted for publication (in a peer reviewed journal). A publications committee will be established to review the multicenter results and develop publications at the completion of the study. The timing of the multicenter publication may be dependent on regulatory submissions and approvals. Individual Sites should coordinate requests for publication through the publications committee or the Sponsor.

7.0 Data Collection and Submission

The Clinical Data Management System (CDMS) for this study will be provided by Medidata Solutions Worldwide, [name].

7.1 Data Collection Methods

This study will report clinical data using the Medidata Rave® web-based application. The Rave® system will be the database of record for the protocol

CONFIDENTIAL INFORMATION

and subject to regulatory inspections. All Rave® users will be trained to use the CDMS and will comply with study specific guidelines/instructions.

Subject data will be collected using protocol-specific electronic case report forms (eCRF). eCRF Guidelines will be provided to sites at the time of database training. Site staff will enter data directly into the eCRF for review by the Sponsor and/or CRO.

